7.1.1 Screening

Screening examination (Visit 1) is to include the procedures found in [Table 7-1](#) and should occur within 28 days prior to baseline. The informed consent must be signed prior to ANY screening procedure being performed. Patients that do not meet eligibility criteria are allowed to be rescreened. The rescreening should be documented in the source files. If the following procedures meet all inclusion and exclusion criteria at the original screening they do not have to be repeated for patients who rescreen within 60 days of baseline (Day 1): vital signs, MRI, and gallbladder ultrasound. Any of these assessments that are abnormal and all other assessments not listed here are to be repeated.

7.1.1.1 Eligibility screening

Manual process: Patient eligibility will be checked by the Registration center once all screening procedures are completed. The eligibility check form will be sent from the site to the Registration center either via fax or email for evaluation. Upon confirmation of eligibility, the Registration center will return the signed eligibility check form and inform assigned treatment arm to the site. Please refer and comply with detailed guidelines in the registration manual.

7.1.1.2 Information to be collected on screening failures

Patients who sign an informed consent but fail to be started on treatment for any reason will be considered a screen failure. The reason for not being started on treatment will be entered on the Screening Log Page. The Demography, Informed consent eCRF pages must be completed for Screen failure patients. No other data will be entered into the clinical database for patients who are screen failures. Please refer to [Section 8.2.2](#) for guidelines on SAE reporting requirements.

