6.5.2 Treatment assignment or randomization

6.5.2.1 Randomization number

If the patient is deemed eligible for the study and will commence dosing, a randomization number will be assigned. Once assigned to a subject, a randomization number will not be reused.

Patients who have prior medications will be assigned randomization numbers [REDACTED] and patients who don't have prior medications will be assigned randomization numbers [REDACTED]

Table 6-4 Treatment assignment numbering

| | With prior medication | Without prior medication |
|-----------------------|-----------------------|--------------------------|
| Randomization numbers | [REDACTED] | [REDACTED] |

Patients will be assigned to one of the 3 treatment arms ([Section 4.1](#) and [Section 6.1](#)) in a ratio of 1:1:1.

Randomization will be stratified by prior medications (i.e. somatostatine analogue and dopamine agonist) (yes or no).

Randomization will be performed using the following procedure to ensure that treatment assignment is unbiased. Random permuted blocks scheme will be used for this study.

A randomization list will be produced by or under the responsibility of Novartis Drug Supply Management using a validated system that automates the random assignment of treatment groups to randomization numbers in the specified ratio. The randomization list will be reviewed by a Biostatistics Quality Assurance Group and locked by them after approval.

Prior to dosing, all patients who fulfill all inclusion/exclusion criteria will be assigned the lowest available number on the randomization list.

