10.1 Analysis sets

10.1.1 Full Analysis Set

The Full Analysis Set (FAS) comprises all patients to whom study treatment has been assigned by randomization. According to the intent to treat principle, patients will be analyzed according to the study treatment they have been assigned to during the randomization procedure.

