4.1.4 Study day

The study day for all assessments (i.e. efficacy, safety) will be calculated as the difference between the date of the event (i.e. visit date, onset date of an event, assessment date) and the first date of study drug plus 1. For patients who got randomized but never dosed, study day is calculated as the difference between the date of event and the date of randomization plus 1.

For any assessment or event such as baseline disease characteristics or medical history that is supposed to occur prior to the start of study drug, the study day will be negative and calculated as the difference between the date of the event and the first date of study drug.

The study day will be displayed in the data listings.

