4.3 Analysis sets

Full analysis set (FAS) comprises of all patients to whom study treatment has been assigned by randomization. According to the intent to treat principle, patients will be analyzed according to the study treatment they have been assigned to during the randomization procedure.

Safety set includes all patients who received at least one dose of study treatment. Patients will be analyzed according to the study treatment according to the treatment they first received.

The rules for patient classification in the analysis sets (FAS and safety) are described hereafter:

T. I. I	D . 41 4 1
Table 4-1	Patient classification rule
I adic T-I	i alieni ciassincation rule

Analysis set	Protocol deviations that cause patients to be excluded from analysis and corresponding deviation codes from VAP Module 3
FAS	No written informed consent prior to any procedure (deviation code = I01)
Safety set	No written informed consent prior to any procedure (deviation code = I01)

The per-protocol set (PPS) and pharmacokinetic analysis set (PAS) discussed on the study protocol, will not be used for the final analysis since there is no pharmacokinetic analysis nor PPS analysis performed and all of them were already reported in [the 12 month CSR].

Although there is no PPS involved, all protocol deviations will be finalized before database lock and reported in the listing.

Analyses of efficacy endpoints will be based on the FAS. Safety analyses will be performed based on the safety set.

5 Statistical methods used in reporting

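### Section 7.1.1.2 classes randomised but undosed patients as screen failures and bars most of their data, although the FAS includes them

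*Protocol*

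**What the plan says.** **Screen failures.** Protocol 7.1.1.2 states: "Patients who sign an informed consent but fail to be started on treatment for any reason will be considered a screen failure". The reason goes on the screening log and the demography and consent pages are completed. Beyond that, "No other data will be entered into the clinical database for patients who are screen failures".

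**Analysis set.** Under Protocol 10.1.1 the FAS "comprises all patients to whom study treatment has been assigned by randomization". SAP 4.3 repeats this, and its Table 4-1 lists one ground for leaving the FAS: no prior written consent. The per-protocol set (Protocol 10.1.3) adds a one-dose condition to FAS membership.

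**Allocation before dosing.** Protocol 6.5.2.1 assigns the randomisation number before the first dose. Under Protocol 7.1.1.1, once eligibility is confirmed, "the Registration center will return the signed eligibility check form and inform assigned treatment arm to the site". Table 7-1 marks the eligibility criteria at screening and again at Visit 2, the day of the first injection.

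**Undosed patients.** SAP 4.1.4 provides for them: "For patients who got randomized but never dosed, study day is calculated as the difference between the date of event and the date of randomization".

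**Primary analysis.** It is done on the FAS (Protocol 10.4.2). A patient without a Month 3 value counts as a non-responder (Protocol 10.4.3, SAP 4.1.9).

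**Rescreening.** Protocol 7.1.1 allows it for patients who fail the eligibility criteria. The patient number is kept (Protocol 6.5.1). On the randomisation number, Protocol 6.5.2.1 says: "Once assigned to a subject, a randomization number will not be reused".

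**The concern.** The same patient falls under two rules that cannot both be followed. Someone randomised and then not dosed is a FAS member by one section and a screen failure with almost no recorded data by another. This can happen after a Visit 2 eligibility finding, or after a refusal once the dose is known in this open-label trial.

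Two things are at stake:

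- **Missing FAS data.** Protocol 10.2 summarises baseline data on the FAS, and Protocol 10.4.4 plans a prior-medication subgroup. SAP 5.5 and 5.6 repeat medical history and prior medication by randomised dose. SAP 5.9.2.2 splits patients by at least 12 weeks of somatostatin-analogue pre-treatment and puts everyone else in a category of others. An undosed patient with no prior-therapy page could fall into that category by default.
- **Omission in practice.** A patient whose record says screen failure is easily left out when the FAS is built. Undosed patients have no Month 3 response, so each omission removes a non-responder and can only raise the rate.

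**Working it through.** **1. Is the class real in the plan?** Yes. Arms are assigned before dosing, eligibility is marked again at Visit 2, the per-protocol set needs a dose condition that the FAS lacks, and the SAP has a study-day rule for these patients.

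**2. Do the rules conflict?**

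| Question about a randomised, undosed patient | Protocol 7.1.1.2 | Protocol 10.1.1, 10.4.3; SAP 4.3, 4.1.9 |
|---|---|---|
| Status | Screen failure | FAS member, by assigned arm |
| Data entered | Demography and consent only | Baseline and prior-medication summaries presuppose more |
| Primary outcome | Not addressed | Non-responder |

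The conflict is over data and labelling. On the primary outcome, the analysis sections decide.

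**3. The plan's own figure.** Inputs from Protocol 10.8: expected rate 30%, dropout 10%, N = 30, minimum 10%.

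- Adjusted rate: 0.30 × (1 − 0.10) = 0.27.
- Expected responders: 30 × 0.27 = 8.1, taken as 8.
- The Clopper-Pearson lower 90% limit for x of n is the 5% quantile of Beta(x, n − x + 1). For 8/30 the interval is 14.0% to 43.0%, so the plan's statement reproduces.
- The fewest responders that clear 10% at N = 30 is 7 (lower limit 11.5%).

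**4. Effect of omitting k undosed patients.** The values of k are assumed, because the documents give no count.

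| Responders, N randomised | k = 0 | k = 1 | k = 2 | k = 3 |
|---|---|---|---|---|
| 8, N = 30: rate | 26.7% | 27.6% | 28.6% | 29.6% |
| 8, N = 30: lower limit | 14.0% | 14.5% | 15.1% | 15.7% |
| 6, N = 30: lower limit | 9.1% | 9.4% | 9.8% | 10.2% |
| 9, N = 33: lower limit | 15.0% | 15.5% | 16.1% | 16.6% |
| 7, N = 33: lower limit | 10.4% | 10.7% | 11.1% | 11.5% |
| 6, N = 33: lower limit | 8.2% | 8.5% | 8.8% | 9.1% |

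Near the planning rate, each omission adds about 1 point to the estimate and about half a point to the lower limit. With 6 responders it adds 0.3 to 0.4 point. At N = 30 the 10% line is crossed only with 6 responders and three omissions. At the 33 actually randomised, 7 responders clear 10% with nobody omitted. With 6 responders it takes six omissions (6/28 = 9.8%, 6/27 = 10.2%).

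**5. Second allocation.** Rescreening is tied to failing eligibility, not to screen-failure status. A patient who declines after learning the dose is therefore not covered. A patient randomised and then found ineligible at Visit 2 fits the wording. The rule against reusing a number stops another patient receiving it, but does not say whether one patient may receive two.

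**The case against.** The strongest reply is that Section 7.1.1.2 concerns data collection and does not define an analysis set. FAS membership rests on randomisation alone, the only listed exclusion is missing consent, and missing Month 3 values are non-responses. A reader might infer that 7.1.1.2 removes randomised patients from the FAS; the documents do not support that. This part of the reply stands.

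A reader might also infer that such patients may be rescreened and draw a second dose. That is not in the text either. Randomisation follows confirmed eligibility, no section provides for a second number, and the unchanged patient number would make a duplicate traceable. The registration manual cited in 7.1.1.1, which is not among the documents, may settle the matter. What remains is silence about the Visit 2 case.

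The reply can add that SAP 5.3 already counts patients randomised and treated, and that the prior-medication stratum can be read from the randomisation number (Table 6-4). Both points are fair. But the stratum does not supply baseline GH or IGF-1, disease history or duration of pre-treatment, and SAP 5.3 asks for neither a count by arm nor a check against the randomisation list.

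**Conclusion.** The point holds as an internal inconsistency. Read literally, Section 7.1.1.2 covers randomised patients who are never dosed and keeps out data that the FAS summaries and subgroups need. The plan still counts these patients as non-responders, so the risk to the primary rate is one of mistaken omission, not of a rule that excludes them.

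The numerical effect is small: about half a point on the lower limit per omitted patient near the expected rate, and decisive only in borderline results. These figures assume numbers omitted and numbers of responders that the documents do not give. They report 33 randomised and no count of undosed patients, so no actual loss is shown. The possibility of a second randomisation is a gap in the text and not a permission.

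**What to change.** 1. In Protocol 7.1.1.2, limit the term screen failure to consented patients who were not randomised.
2. Require screening and baseline data to be entered for any patient randomised but not dosed.
3. State in Protocol 6.5.2.1 or 7.1.1 that a patient is randomised only once and is analysed under the first assignment.
4. In SAP 5.3, report randomised-not-treated patients by arm, and reconcile the FAS count with the randomisation list before lock.

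Amendment 3 reports enrolment complete, and the SAP says the primary rate is already in the 12-month report. The useful step now is therefore the reconciliation: with 33 randomised, the FAS should be 33 unless a patient lacked prior consent. Baseline data for anyone found missing can be entered as far as site records hold them.

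The cost is a few sentences, one check and a little data entry. If a patient had been left out, the stated rate would become slightly less favourable.

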7.1.1.3 Patient demographics and other baseline characteristics

Standard demographic information and medical history will be collected. Acromegaly or pituitary gigantism history and diabetes history together with the medication/treatment used will also be collected. Other baseline assessments will be collected as per [Table 7-1](#).

7.1.2 Treatment period

The treatment period in the core phase of the study will be 12 months. Patients will have monthly visits with some visits more frequently (see [Table 7-1](#)). All visits should be performed on the indicated days. In cases where this is not possible, the following visit windows apply: +/- 2 days for visits 4-20 and 777, -2/+7 days for the 778, 779 and extension phase. Efforts should be made to have pasireotide LAR administration occurring as indicated in [Table 7-1](#) and [Table 7-2](#) at approximately the same time of day at each occurrence.

7.1.3 End of treatment visit including study completion and premature withdrawal

Patients who discontinue study treatment before visit 777 (if patient is in the core phase of the study) or visit 33 (if patient is in the extension phase of the study), should be scheduled for a visit as soon as possible, at which time all of the assessments listed for the visit 777 / 778 will be performed ([Table 7-1](#) and [Table 7-2](#)). An End of Treatment eCRF page should be completed, giving the date and reason for stopping the study treatment.

At a minimum, all patients who discontinue study treatment, including those who refuse to return for a final visit, will be contacted for safety evaluations (visit 779) during 56 days following the last dose of study treatment.

Patients who discontinue study treatment should be considered withdrawn from the study after the final visit assessments are performed or when it is clear that the patient will not return for these assessments.

If a study withdrawal occurs, or if the patient fails to return for visits, the investigator must determine the primary reason for a patient's premature withdrawal from the study and record this information on the End of Treatment eCRF page. The investigator must inform the premature withdrawal to Novartis.

For criteria for premature withdrawal refer to [Section 7.1.3.1](#).

End of treatment visit and Study completion visit for patients treated for more than 2 years (after Visit 33)

If a patient discontinues after 2 years of treatment (after Visit 33), only the assessments with an asterisk in [Table 7-2](#) need to be performed on visit 778 and visit 779.

7.1.3.1 Criteria for premature patient withdrawal

Patients may voluntarily withdraw from the study or be dropped from it at the discretion of the investigator at any time. Patients may be withdrawn from the study if any of the following occur:

- Adverse event(s) [including abnormal laboratory value(s) and abnormal test procedure result(s)]
- Protocol deviation (including but not limited to, new therapy for acromegaly, and discovery of patient ineligibility)
- Patient withdrew consent

- Lost to follow-up
- Administrative problems
- Death
- Disease progression
- Pregnancy
- Treatment duration completed as per protocol

The investigator must also inform the premature withdrawal to Novartis, if this occurs during the core period.

In addition to the general withdrawal criteria, the following **study specific criteria** will also require study treatment discontinuation:

- Patients experiencing unacceptable toxicity, as described in [Table 6-2](#), [Table 6-3](#).
- Patients unable to tolerate the lowest dose (20 mg) as per [Section 6.3](#).
- Patients with > 28 consecutive days of treatment interruption (either due to tolerability, investigator decision or patient compliance)
- Uncontrolled diabetes mellitus, consistently high glucose values FPG \geq 240 mg/dL (13.3 mmol/L) or HbA1c value \geq 10 % despite prior appropriate management and prior dose adjustment of the study drug,
- Patients experiencing adverse events in QTc:
 - a confirmed QTcF $>$ 470msec and discontinuation recommended by a cardiologist, or
 - Mean QTcF $>$ 500 msec measured by triplicate ECGs
 - Significant arrhythmia findings from Holter monitoring such as:
 1. Any ventricular or supra-ventricular tachyarrhythmia associated with symptoms of hemodynamic compromise
 2. Sustained ventricular tachycardia ($>$ 30 sec) irrespective of symptoms
 3. Recurrent non-sustained ventricular tachycardia (\geq 3 beats) during any 24-hour monitoring period
 4. Torsades de Pointes
 5. Cardiac arrest
 6. Pause $>$ 5 seconds
 7. Second or third degree AV block
 - New occurrence of clinically significant/symptomatic bradycardia, or
 - Increased risk of QT prolongation by use of QT prolonging medication, or
 - Hypokalemia ($<$ 3.5 mmol/L) or hypomagnesaemia ($<$ 0.7 mmol/L) confirmed by repeat testing that is either a new finding or accompanied by vomiting or diarrhea and not corrected by treatment.
- Patients experiencing the abnormal hepatic criteria below:
 - ALT or AST $>$ 3 x ULN and Total Bilirubin \geq 2 x ULN and ALP $<$ 2 x ULN
 - ALT or AST $>$ 5 x ULN and \leq 8 x ULN persistent for more than 2 weeks

- ALT or AST > 8 x ULN
- Lack of efficacy: during the core phase treatment period, patients with GH level > 2.5ug/L and/or IGF-1 > ULN (age and sex related) be discontinued from the study unless clinical benefit has been observed as per the investigator's judgment.

Patients who withdraw prematurely from the core phase cannot participate in the extension phase.

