These changes must be recorded on the Dosage Administration Record CRF.

Dose interruption

If a patients requires a dose interruption of >28 days from the intended day of the next scheduled dose (>56 days from the previous dose), then the patient must be discontinued from the study.

Table 6-1 Dose titration steps for pasireotide LAR

| | Dose level 0 | Dose level 1 | Dose level 2 |
|-----------------------|--------------|-----------------------------|-----------------------------|
| Dose increase | | | |
| SOM230 LAR | 60 mg | Not applicable ¹ | Not applicable ¹ |
| SOM230 LAR | 40 mg | 60 mg | Not applicable ¹ |
| SOM230 LAR | 20 mg | 40 mg | 60 mg |
| Dose reduction | | | |
| SOM230 LAR | 60 mg | 40 mg | 20 mg |
| SOM230 LAR | 40 mg | 20 mg | Not applicable ² |
| SOM230 LAR | 20 mg | Not applicable ² | Not applicable ² |

¹ Dose increase above 60 mg is prohibited.

² Dose reduction below 20mg is prohibited. Dose reduction should be based on the worst toxicity demonstrated at the last dose.

Table 6-2 Guideline for treatment of patients experiencing adverse events

| Adverse event | Action |
|---|---|
| AE CTC grade ≤ 2 | No drug adjustments |
| AE CTC grade ≥ 3 and assessed as study drug related | Reduce pasireotide LAR i.m. dose from 60 mg to 40mg 40 mg to 20mg 20 mg - discontinue If AE improves to grade ≤ 2 before the next administration, increase dose to that prior to the dose reduction unless investigator opinion is to remain on current dose. If the dose is increased and the AE recurs at CTC grade ≥ 3, the dose should be reduced again and the patient should stay on this lower dose and no further dose titrations are allowed. If AE does not improve to grade ≤ 2 on the minimum dose the patient will be withdrawn. |

For the management of QT prolongation and LFT increases refer to specific instructions provided in Special Safety in [Section 6.3.3 \(Figure 6-2 and Figure 6-3\)](#).

Table 6-3 Guideline for treatment of patients experiencing adverse events in QTcF

| Adverse event | Action |
|--|--|
| CTC grade 1 (QTcF ≤ 470 msec) | No study drug adjustments |
| CTC grade 2 (470 < QTcF ≤ 500 msec) | No study drug adjustments Patient is to be referred to a cardiologist for evaluation and appropriate management. Patient can remain in the study (unless discontinuation is recommended by cardiologist) |

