Close and frequent monitoring of blood glucose is needed during pasireotide treatment. The principal investigator is to educate the patient on the signs and symptoms of hyperglycemia. Patients must monitor their fasting blood glucose by fingerstick at home at least 3 times per week for the first month of pasireotide LAR treatment. If a patient does NOT have any fasting values above 100 mg/dL, monitoring can be decreased to at least 2 times per week for months 2 and 3 and 1 time every 2 weeks for 4 months through 6 months. If glucose values remain normal (lower than or equal to 100 mg/dL), monitoring is at the investigator's discretion after 6 months. If any values are observed above 100 mg/dL, the guidelines in [Figure 6-1](#) are to be followed. These guidelines are based on the current recommendations from the 2012 American Diabetes Association and European Association for the Study of Diabetes aiming at a glycemic treatment goal of FPG <130 mg/dL (<7.2 mmol/L). Appropriate actions such as initiation of anti-hyperglycemic therapy (and referral to diabetes specialist) are to be taken by the investigator as outlined on [Figure 6-1](#). If fasting blood glucose values dictate initiation of anti-hyperglycemic treatment (i.e., confirmed >130 mg/dL by self-monitoring), a fasting plasma glucose sample using the local laboratory is to be collected prior to initiation of anti-hyperglycemic treatment. If a patient has a dose increase, monitoring for hyperglycemia should follow the recommendations for the first month of treatment and continue as presented above for subsequent months.

[figure not shown]
It is recommended that the patients be encouraged to keep a diary for their blood glucose for appropriate management throughout the study and present the collected data to their physician/diabetes specialist for evaluation. This data will not be collected by the sponsor.

In addition to self-monitoring, fasting plasma glucose and HbA1c will be collected at study visits per [Table 7-1](#) and [Table 7-2](#). Intervention for hyperglycemia is to be implemented in any patient meeting any of the following criteria: FPG > 130 mg/dL or HbA1c ≥ 6.5 %.

Patients with FPG > 160 mg/dL or HbA1c >7.5% despite adjustment of antidiabetic therapy should be referred to a diabetes specialist (or earlier per investigator’s judgment).

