As outlined in [Table 6-2](#), patients with grade 3 hyperglycemia (FPG value >250 mg/dL; >13.9 mmol/L) at any point in the study should have the dose of pasireotide decreased. Patients who in spite of appropriate therapeutic interventions and despite dose reduction of study drug develop uncontrolled diabetes mellitus and/or consistently high blood glucose values: FPG ≥ 240 mg/dL (13.3 mmol/L) or HbA1c value ≥ 10 % will require study treatment discontinuation as outlined in [Section 7.1.3.1](#).

Figure 6-1 Fasting self-monitoring blood glucose guidelines

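### The mandatory glucose stop presupposes a prior dose reduction, which a patient still on a 20 mg starting dose cannot have had

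*Protocol*

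**What the plan says.** Section 7.1.3.1 lists study-specific criteria under which treatment must be discontinued. The glucose criterion covers uncontrolled diabetes and consistently high values (FPG ≥ 240 mg/dL or HbA1c ≥ 10%), with the condition "despite prior appropriate management and prior dose adjustment of the study drug". Section 6.3.3.1 gives the same rule for patients who, with appropriate treatment and "despite dose reduction of study drug develop uncontrolled diabetes mellitus and/or consistently high blood glucose values: FPG ≥ 240 mg/dL" or HbA1c ≥ 10%.

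The dose rules in Section 6.3.1 set the background:

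- 20 mg is the floor. The footnote to Table 6-1 states: "Dose reduction below 20mg is prohibited".
- Table 6-2 reads "AE CTC grade ≤ 2 | No drug adjustments" for mild and moderate events. For a drug-related event of grade 3 or above it gives "20 mg - discontinue".
- For glucose, Section 6.3.3.1 ties grade 3 to FPG and refers to Table 6-2. Its instruction is that anyone who has "grade 3 hyperglycemia (FPG value >250 mg/dL; >13.9 mmol/L) at any point in the study should have the dose of pasireotide decreased".
- HbA1c has a level for intervention (≥ 6.5%), for referral (> 7.5%) and for the stop (≥ 10%), but none for dose reduction.

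Section 7.1.3.1 also has a separate mandatory criterion, "Patients unable to tolerate the lowest dose (20 mg) as per" Section 6.3, and allows withdrawal at the investigator's discretion at any time. Section 4.1 randomises patients 1:1:1 to 20, 40 or 60 mg.

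**The concern.** A required safety stop should be reachable at every dose in the trial. Here the condition assumes that the dose can be lowered first, which is true for patients on 40 or 60 mg but not for a patient still on a 20 mg starting dose. Two patients on the same dose with the same glucose values can then fall under different rules because of their dose history alone, and the protocol gives no reason for the difference.

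Hyperglycaemia is the main known safety difference of this drug. In the phase III study described in Section 1.2.1.2 it was reported in 28.1% on pasireotide LAR and 8.3% on octreotide LAR, with grade 3 or 4 diabetes mellitus in 5.6% and 0%. In the Japanese volunteer study, 3 of 8 subjects had a glucose increase reported after a single 20 mg dose. By contrast, the stops in the same list for a mean QTcF above 500 msec and for ALT or AST above 8 × ULN carry no dose-reduction condition.

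At stake are patient safety and consistent discontinuation across sites.

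**Working it through.** **Thresholds.** At 18 mg/dL per mmol/L, 240/18 = 13.33 and 250/18 = 13.89, which agree with the protocol's 13.3 and 13.9 mmol/L. The levels are correctly stated.

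**Applying the rules.** The explicit glucose stop needs (a) FPG consistently ≥ 240 mg/dL or HbA1c ≥ 10%, (b) appropriate management, and (c) a prior dose reduction. The table assumes (b) is met. The Table 6-2 column grades the event on FPG alone, with grade 3 at FPG > 250 mg/dL; this is a simplification.

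| Patient on 20 mg | FPG (mg/dL) | HbA1c | Explicit glucose stop | Table 6-2 |
|---|---|---|---|---|
| Never reduced | 245 | 9% | not met | no adjustment |
| Never reduced | 230 | 10.5% | not met | no adjustment |
| Never reduced | 260 | 9% | not met | discontinue, if drug related |
| Reduced from 40 mg | 245 | 9% | met | no adjustment |
| Reduced from 40 mg | 230 | 10.5% | met | no adjustment |

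The first two rows are the gap. The third is not, because Table 6-2 closes it. Rows 4 and 5 repeat the values of rows 1 and 2 and give the opposite result.

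**Does the looser word in Section 7.1.3.1 help?** An adjustment could be read to include an increase. A patient raised from 20 to 40 mg would then satisfy Section 7.1.3.1 but not Section 6.3.3.1. It does not help a patient whose dose has stayed at 20 mg, unless an interruption is counted as an adjustment, which neither section says.

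**Who is exposed, and when.** The SAP (Section 2) gives 33 randomised patients, so 33/3 = about 11 start on 20 mg. Up-titration begins at Month 3 (Day 85), so until then they stay on that dose. From Month 3, uncontrolled 20 mg patients without tolerability issues go to 40 mg and can later be reduced, so the exposed group shrinks. Controlled patients stay on 20 mg: with the 30% response rate at 20 mg in the earlier patient study, 11 × 0.30 = 3.3, or about 3. Non-responders held at 20 mg for tolerability come on top; their number is not given.

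Table 7-1 schedules on-treatment fasting glucose at Days 22, 29, 57, 85 and every later core visit, and HbA1c at Days 85, 169, 253 and 337. With scheduled tests, the HbA1c part can therefore apply only from Day 85.

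**The case against.** The strongest reply is that such a patient would not in practice be left on treatment. Four parts of it deserve weight.

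- **Grading.** Section 8.1.1 asks for a diagnosis where possible, and the phase III results list grade 3 or 4 diabetes mellitus separately from hyperglycaemia. Uncontrolled diabetes with HbA1c ≥ 10% may well be graded 3 and judged drug related, and Table 6-2 then stops a 20 mg patient. This narrows the gap but leaves it to depend on the grade a site assigns.
- **Other routes.** The criterion on intolerance of 20 mg, and investigator discretion, can both end treatment. That stands. Neither sets a glucose level, so neither replaces the mandatory rule.
- **Earlier steps.** Diabetic patients with HbA1c > 8% are excluded, intervention starts at FPG > 130 mg/dL or HbA1c ≥ 6.5%, and "Patients with FPG > 160 mg/dL or HbA1c >7.5% despite adjustment of antidiabetic therapy should be referred to a diabetes specialist". These make the case rarer.
- **Figure 6-1.** It is not shown and could add an action on the FPG side. By its title it covers fasting self-monitoring, so it is unlikely to settle the HbA1c side.

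Three stronger readings are tempting, and the documents do not support them.

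- A reader might infer that a stop at 240 below a reduction trigger at 250 mg/dL is an ordering error. It is coherent: a single value above 250 triggers a reduction, while the stop concerns consistently high values after treatment and reduction. A patient reduced at 260 who stays at 245 should stop.
- A reader might infer that patients on 40 or 60 mg are also blocked. Sections 2.2, 4.1 and 6.1.1 permit reduction for any tolerability problem at any time, so they can reach the stop.
- A reader might take the 5.6% rate of grade 3 or 4 diabetes mellitus as a ceiling for the gap. Those events are of a grade that Table 6-2 already handles, and they arose in patients started on 40 mg, so the figure neither estimates nor bounds the gap.

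**Conclusion.** The point holds in a narrow form. A patient on 20 mg who has never been reduced, with no drug-related grade ≥ 3 event, does not meet the explicit glucose stop at values that require a patient reduced to 20 mg to discontinue. About 11 of 33 patients start in the exposed position, and fewer remain there after Month 3. How many would reach these glucose values cannot be derived from the documents; the number is probably very small.

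The conclusion rests on reading Section 6.3.3.1 as defining the adjustment meant in Section 7.1.3.1, and on Figure 6-1 not closing the FPG part. It concerns patient safety and consistent discontinuation. Sample size, power and alpha are not touched. It is a wording correction to consider, not a flaw in the design.

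**What to change.** Use the same condition in Sections 6.3.3.1 and 7.1.3.1: *despite appropriate management and prior dose reduction of the study drug, or if the patient is already on 20 mg*. Make clear that appropriate management is still expected of the 20 mg patient; only the reduction requirement falls away. Saying dose reduction in both places also prevents an up-titration from counting as the adjustment.

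The thresholds, Table 6-2 and the general permission to reduce can stay as they are. An HbA1c-triggered reduction at 40 or 60 mg would be a new clinical rule and is not needed here.

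The cost is a few words in two sections, made by a written amendment under Section 12.1. No new visits, data or analyses are needed, because Tables 7-1 and 7-2 already schedule fasting glucose and HbA1c through Month 24.
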